5.1.6. Study Drug Administration

Dosing is based on the weight obtained on Day 1 and every 12-weeks thereafter. The total dose **is not to exceed 4.1g**. The total **volume of fluid is not to exceed 410 mL**. Study Drug is administered by IV infusion, using an infusion set with a sterile, nonpyrogenic, low-protein-

binding in-line filter (0.2-micron pore size). The infusion and post-infusion observation periods are provided in Table 1 below.

Table 1 Pamrevlumab (or placebo): Dose, Route, and Administration

Agent	Dose	Route	Infusion Rate	Frequency
Pamrevlumab/ matching placebo	30 mg/kg	IV	
 • First Infusion (including first infusion in OLE) : Infuse over approximately 2 hours. • Second Infusion (including second infusion in OLE): If first infusion is well tolerated, infuse over approximately 1 hour. • Subsequent Infusions: If 1 hour infusion(s) are well tolerated, infuse over approximately 30 minutes. 
For ALL infusions: A Post-infusion observation period has to be included throughout the study: It is 1 hour for at least the first 3 infusions (including in OLE); this may be reduced to 30 minutes if there were no infusion-related AEs after the first 3 infusions.
 
For Czech Republic only: A Post-infusion observation period has to be included throughout the study: 2 hours for the first 3 infusions; this may be reduced to 30 minutes if there were no infusion-related AEs after the first 3 infusions
	
Day 1 and Every 3 weeks thereafter
 
NOTE: Infusions must be AT LEAST 10 days apart

NOTE: DO NOT ADMINISTER STUDY DRUG AS AN IV PUSH OR BOLUS INJECTION, OR CONCURRENTLY IN THE IV LINE WITH OTHER AGENTS.

The first infusion should be completed in approximately 2 hours. If the first infusion is well tolerated and no infusion-associated AEs are observed during the infusion and observation period, the second infusion should be completed in approximately 1 hour. The subsequent infusion periods may be shortened to approximately 30 minutes, if no infusion-associated AEs were observed during the initial two infusions.

If an infusion-associated AE occurs during any of the subsequent infusions, study drug will be administered over approximately 1 hour for the next three infusions. If no infusion associated AEs are observed in any of these three infusions, the infusion may be decreased again to approximately 30 minutes.

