The Investigator or other qualified personnel must be either present, or immediately available, during all infusions and observation periods for each subject. If a subject has a significant infusion associated AE, the infusion rate may be slowed or temporarily stopped, depending on the severity of symptoms. If such a subject continues study drug dosing, a physician should be immediately available during all subsequent infusions and observation periods at the site.

Subjects who experience an infusion associated AE will not be allowed to participate in Home Health Care (HHC). In addition, if a subject experiences a life-threatening (per Section 7.3.3) infusion-associated AE, study drug treatment must be permanently discontinued (see [Section 4.3](#)).

The Investigator has the option to use premedication, e.g., antihistamines, nonsteroidal anti-inflammatory drugs (NSAIDs) for a subsequent infusion: this may be discussed with the FibroGen Medical Monitor or designee.

Infusions are to be continued until the total volume has been administered. Subjects will remain at the study site for 1 hour (2 hours for Czech Republic Only) after the end of the infusion for clinical observation. This post-infusion observation period may be reduced to 30 minutes if the subject has had no infusion-associated AEs during the first three infusions.

Study drug will be administered at a hospital or ambulatory setting with adequate facilities for managing medical emergencies. Medications for the treatment of acute reactions, including anaphylaxis, must be available to study site staff for immediate use. There is no specific treatment for a pamrevlumab overdose or infusion-associated AEs. Signs and symptoms should be managed with appropriate standard of care treatment.

The Sponsor may consider the use of properly trained home health care staff to administer the infusions of study drugs at the subject's home and corresponding study assessments during the conduct of the study (after the completion of at least three 30-minute infusions without safety concerns), consistent with institutional regulations and policies. See Section 5.1.7 for details.

COVID-19 Vaccine and Study Drug Administration

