5.1.7. Home Health Care

The Sponsor may consider the use of properly trained and qualified home health care staff in specific regions/countries, depending on local acceptance and adoption of home visits, to administer study drug at the subject's home, after completion of at least the first three infusions without safety concerns. Home Health Care (HHC) is optional and the decision to utilize this service is determined by the site, consistent with institutional regulations and policies.

NOTE: Subjects who experience a significant infusion-associated AE may not receive HHC. In addition, if a new safety concern arises during a home infusion, the subject has to attend an on-site visit for an Investigator assessment as soon as feasible. HHC support will only be on weeks

with study drug infusions and no scheduled study assessments. Visits that include collection of PFT, ePRO, safety labs or HRCT must be performed on-site. Medications and supplies to treat suspected hypersensitivity/anaphylactic reactions must be available for immediate use for all study drug infusion visits.

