Each subject will receive pamrevlumab (30 mg/kg) every 3 weeks, using the weight obtained on Day 1 of the OLE phase (=EX Day 1), and every 24 weeks thereafter, for assessment of the proper weight-based dosing regimen. EX Day 1 is expected to be scheduled 3 weeks \pm 7 days after the Week 48 visit of the main study.

See Protocol Section 5 for detailed information on study drug infusions. Home infusions via home health care (HHC) may be available during the OLE phase of the study at the discretion of the Investigator but such home infusions services will not be reimbursed by the Sponsor. Any home infusions via home health care are not permitted until at least three infusions in the OLE period have been administered without safety concerns.

Subjects who experience a significant infusion-associated AE may not receive HHC. In addition, if a new safety concern arises during a home infusion, the subject has to attend an on-site visit for an Investigator assessment as soon as feasible.

Medications and supplies to treat suspected hypersensitivity/anaphylactic reactions must be available for immediate use for all study drug infusion visits.

Important NOTE: The infusion durations and post-infusion observations periods have to be followed per Table 1 in Protocol Section 5.1.6, including the initial dosing and observations periods. This is to ensure that subjects transitioning from placebo (in the double blinded phase) receive adequate safety monitoring during OLE.

Visit windows are within ± 7 days of the scheduled visit date from OLE (EX) Week 3 through last dose in the OLE; however, visits should be at least 10 days apart, to ensure intervals of at least 10 days between study drug infusions.

All study visits will be performed in accordance with the OLE Schedule of Assessments (SOA) presented in Appendix 6.

Missed Visits/Missed Doses

Scheduled visit dates are determined from the time of the first dose in OLE, which is defined as EX Day 1. If a subject misses a visit, the subject should resume the regular visit schedule at the next scheduled visit.

Missed doses are not to be made up through extra visits. If a subject misses more than two infusions in any 18-week period, or two sequential infusions, the FibroGen Medical Monitor should be notified. The reason for missed doses must be documented in the subject's clinical record.

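### Protocol Sections 5.1.6 and 5.1.7 set different start conditions for home infusion, so in the main phase the Week 9 dose can be given at home under one and not under the other

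*Protocol*

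**What the plan says.** Three places in the protocol say when home infusion may begin.

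- **Section 5.1.6 (Study Drug Administration)** lets the sponsor consider home administration while the study is being conducted, "after the completion of at least three 30-minute infusions without safety concerns", and refers to Section 5.1.7 for details.
- **Section 5.1.7 (Home Health Care)** allows it "after completion of at least the first three infusions without safety concerns". It states no duration. It also keeps on site any visit with lung function tests, electronic questionnaires, safety laboratory tests or HRCT, and makes home care optional and a decision for the site.
- **Appendix 6 (OLE)**, in its dosing instructions and again in footnote e of its schedule, states a prohibition: "Any home infusions via home health care are not permitted until at least three infusions in the OLE period have been administered without safety concerns". It too states no duration.

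Infusion durations are set in Table 1 and the text below it in Section 5.1.6: "The first infusion should be completed in approximately 2 hours"; if that goes well, "the second infusion should be completed in approximately 1 hour"; and "The subsequent infusion periods may be shortened to approximately 30 minutes, if no infusion-associated AEs were observed during the initial two infusions". Appendix 6 repeats this sequence for the OLE: "The infusion durations and post-infusion observations periods have to be followed per Table 1 in Protocol Section 5.1.6, including the initial dosing and observations periods".

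**The concern.** The two main-phase conditions would be equivalent only if the first three infusions were all 30-minute infusions, and the protocol's own duration schedule rules that out. A site that follows the pointer from 5.1.6 to the section actually titled Home Health Care finds the earlier threshold. A home dose given on that basis complies with 5.1.7 and not with 5.1.6, so the same act may or may not be recorded as a deviation, depending on which section the monitor reads.

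The condition is a safety gate. Under 5.1.7 a subject may move to home dosing after a single infusion at the shortest duration; under 5.1.6, after three. Infusion 4 is also the first at which Table 1 lets the post-infusion observation period fall to 30 minutes, so the earlier threshold coincides with the first possible reduction in observation.

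**Working it through.** The plan gives no figure for the earliest home dose, so the check is a count.

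**Inputs**

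- Dosing is every 3 weeks from Day 1 (Appendix 1, footnote g), so infusion k falls at Week 3 × (k − 1). For the Week 48 dose, k = 48/3 + 1 = 17, which matches the protocol's total of up to 17 infusions.
- Durations on the fastest path (Table 1): about 2 h, about 1 h, then about 30 min from infusion 3.
- On-site visits: lung function at Weeks 6, 12, 18, 24, 36 and 48 (SAP for the double-blind period, Table 7); laboratory tests and questionnaires at Weeks 12, 24, 36 and 48 (SAP Tables 9 and 10); HRCT at Weeks 24 and 48 (SAP Table 8).

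**Main phase, fastest path**

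| Infusion | Week | Duration | 30-min infusions completed before this one | Home allowed by 5.1.7 (3 infusions done)? | Home allowed by 5.1.6 (three 30-min infusions done)? | On site anyway? |
|---|---|---|---|---|---|---|
| 1 | 0 | 2 h | 0 | No | No | Yes |
| 2 | 3 | 1 h | 0 | No | No | No |
| 3 | 6 | 30 min | 0 | No | No | Yes (lung function) |
| 4 | 9 | 30 min | 1 | **Yes** | **No** | No |
| 5 | 12 | 30 min | 2 | Yes | No | Yes (lung function, labs, questionnaires) |
| 6 | 15 | 30 min | 3 | Yes | Yes | No |

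The thresholds differ by two infusions (4 against 6), or 15 − 9 = 6 weeks. Week 12 is on site under either rule, which leaves one disputed home dose per subject, at Week 9.

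Shortening to 30 minutes is optional. If infusion 3 were kept at 1 hour and infusions 4 to 6 ran at 30 minutes, 5.1.6 would be met only after infusion 6 (Week 15). Weeks 9 and 15 would then both be in dispute. The fastest path is therefore the smallest gap.

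**OLE**

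Appendix 6 is met after three OLE infusions, so its earliest home dose is OLE infusion 4, at EX-Week 3 × (4 − 1) = 9. What 5.1.6 adds depends on how its count is read:

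- If it starts again at EX Day 1, three 30-minute OLE infusions are complete after OLE infusion 5, and the earliest home dose is infusion 6, at EX-Week 3 × (6 − 1) = 15.
- If it carries over, a subject who had three uneventful 30-minute infusions in the main phase meets 5.1.6 on entering the OLE. Appendix 6 is then the only limit, and both rules are satisfied at EX-Week 9.

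**The case against.** Both main-phase clauses are minima attached to something the sponsor may consider, so a site that waits for the longer one satisfies both. Home care is optional and limited to certain regions or countries. Section 5.1.7 also has its own safeguards: trained staff, reaction medication at hand for every infusion visit, and an on-site assessment after any new safety concern at home. Subjects with an infusion-associated adverse event are barred from home care under 5.1.6, and those with a significant one under 5.1.7. All of this stands and keeps the practical effect small. It does not remove the conflict: only a site that reads both sections can choose the longer wait, and 5.1.6 directs readers to the section with the earlier threshold.

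The objection is strongest on the OLE. A reader might infer that two OLE home doses, EX-Weeks 9 and 12, are in dispute, and that for subjects coming from placebo these are the fourth and fifth doses of active drug. The documents do not support that as a firm statement. Table 1 says expressly that infusion durations and observation start again in the OLE; the home-care sentence in 5.1.6 says nothing of the kind about its count. Placebo infusions are infusions of blinded study drug, so 30-minute infusions in the main phase may count. Appendix 6 is also a specific rule whose text and footnote agree with each other.

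A reader might also infer that 5.1.7 and Appendix 6 expressly accept infusions of any duration. They are silent on duration, and Appendix 6 is worded as a prohibition up to a point and grants no permission. Nor is a subject held indefinitely at 1-hour infusions a typical case: Table 1 moves to 30 minutes once 1-hour infusions are tolerated.

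**Conclusion.** The main-phase contradiction holds. Sections 5.1.6 and 5.1.7 give different answers to whether infusion 4 at Week 9 may be given at home, and no other part of the protocol settles it. On the fastest path the size is one dose per subject who uses home care, with one 30-minute infusion completed beforehand against three. This rests on the Table 1 durations and on taking the list in 5.1.7 (lung function, questionnaires, safety labs, HRCT) as what keeps a visit on site. The number of subjects affected cannot be given, because uptake of home care is not stated.

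For the OLE the finding is an ambiguity, not a demonstrated conflict. For a subject who already has three uneventful 30-minute infusions from the main phase, EX-Week 9 and EX-Week 15 are rival dates only if the 5.1.6 count starts again at EX Day 1, which the documents do not say.

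**What to change.** Reconcile Sections 5.1.6 and 5.1.7 so that a single start condition for home infusion applies in the main phase, stated as a number of infusions and, if duration is meant to matter, their duration. In Appendix 6, both in the dosing instructions and in footnote e, state whether the 5.1.6 condition also applies in the OLE and, if so, whether its count starts again at EX Day 1. Which condition stands is for the sponsor's medical team.

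The cost is a sentence or so in each of these places at the next amendment. On the fastest path, a subject using home care would have at most one on-site infusion more or fewer in the main phase than under the section their site now follows. No analysis or sample-size figure changes.

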5.1.7. Home Health Care

The Sponsor may consider the use of properly trained and qualified home health care staff in specific regions/countries, depending on local acceptance and adoption of home visits, to administer study drug at the subject's home, after completion of at least the first three infusions without safety concerns. Home Health Care (HHC) is optional and the decision to utilize this service is determined by the site, consistent with institutional regulations and policies.

NOTE: Subjects who experience a significant infusion-associated AE may not receive HHC. In addition, if a new safety concern arises during a home infusion, the subject has to attend an on-site visit for an Investigator assessment as soon as feasible. HHC support will only be on weeks

with study drug infusions and no scheduled study assessments. Visits that include collection of PFT, ePRO, safety labs or HRCT must be performed on-site. Medications and supplies to treat suspected hypersensitivity/anaphylactic reactions must be available for immediate use for all study drug infusion visits.

5.1.8. Missed Dose

Every attempt should be made to complete all study visits within the windows as outlined in the Schedule of Assessment (SOA) ([Appendix 1](#)).

Scheduled visit dates are determined from the time of the first dose, which is defined as Day 1. A visit schedule is provided in Section 6.1.2 and the SOA ([Appendix 1](#)). Visits conducted outside the visit windows will be recorded as a protocol deviation. Missed doses are not to be made up through extra visits. If a subject misses more than two infusions in any 18-week period throughout the study, or two sequential infusions, the FibroGen Medical Monitor should be notified. The reason for missed doses must be documented in the subject's clinical record.

If a dose is missed due to a missed visit, see [section 6.1.4](#) and [6.1.5](#).

Refer to the case report form (CRF) completion guidelines for additional information on CRF completion requirements for missed visits.

5.1.9. Study Drug Handling and Disposal

All study drug provided by the Sponsor should be retained at the site until otherwise instructed in writing by the Sponsor (or designee). If local/regional/institutional policies do not allow the site to retain study drug, the site must provide the Sponsor (or designee) their drug destruction SOP/process for review and approval. The Sponsor (or designee) will perform drug accountability and reconciliation for all study drug received at the site prior to approving study drug return/destruction. Upon completion of accountability/reconciliation or upon completion of the study or termination of the investigational site, all used, unused, partially used study drug, and all study drug that was not dispensed will be shipped to a destruction site designated by the Sponsor (or designee) for destruction. IV bags used to infuse study drug can be disposed of per institutional policy. Please refer to the IP Manual for additional information on study drug materials, management and accountability.

5.1.10. Co-Administration of an Approved IPF Therapy

During the treatment period, co-administration of an approved IPF therapy (i.e., pirfenidone or nintedanib) is acceptable if clinically indicated in the Investigator's opinion, provided that the Investigator assesses the potential risks/benefits of combining approved IPF therapies with blinded study treatment.

Dosing of approved IPF therapy, and safety monitoring while receiving such therapy, must be in accordance with the approved therapy's local label.

5.1.11. Treatment Compliance

All treatments are administered at the investigational site by qualified personnel and documented in the corresponding case report form (CRF).

5.2. Concomitant Medications

5.2.1. Permitted Concomitant Medications

Concomitant medications (any prescription and/or over-the-counter [OTC] preparation) and procedures or nondrug therapies (e.g., physical therapy, acupuncture, continuous positive airway pressure [CPAP]) used by a subject while participating in this clinical trial must be recorded from the Screening Visit through 28 days after the last dose. If the subject experiences an AE or SAE before the end of the final safety phone call (60 days after last dose), concomitant medications and nondrug therapies may also be collected, if part of the treatment of the AE/SAE.

Other than the restrictions that follow, concomitant medications may be given at the discretion of the Investigator. It is expected that Investigators will provide optimal medical care for the subject's various co-existing medical conditions. The Investigator should ensure optimal medical care is provided the course of the study.

Oral prednisone or equivalent oral corticosteroid: up to 10 mg daily for chronic use is permitted, as long as such use is for a condition other than IPF, and has to be documented accordingly. Higher doses for acute conditions are permitted. N-acetylcysteine (NAC): up to 1800 mg daily, is also permitted during the study.

COVID-19 vaccination is permitted during the study. Refer to section 5.1.6 for additional details, for the recommended timing between COVID-19 vaccinations and study drug dosing.

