- a.) Plans to re-screen a subject must be discussed with, and approved by, the Medical Monitor prior to re-screening.
- b.) Visit window of ±7 days, Week 3 through Week 48. The visit window of ±7 days also applies to assessments that cannot be performed on the same day; these assessments are considered part of that specific visit, and are to be labelled as such. Missed visits are not to be made up between scheduled visits, subject is to return for the next scheduled visit.
- c.) Unscheduled visit assessments (procedures) performed as necessary. During the COVID-19 pandemic, the visit modality (e.g.: in-person versus remotely) and scheduling maybe adjusted and conducted at the discretion of the Investigator, in accordance with the site’s rules and recommendations, and using all necessary precautions. If a visit has to be done remotely it can be conducted with any technology available to the site and study subjects.
- d.) Height is measured only at screening. Weight is measured at screening, Day 1(to calculate the starting dose), and every 12 weeks thereafter to determine the need for dose adjustment.
- e.) Additional PE’s may be performed as needed, if clinically indicated.

- f.) Additional ECGs may be performed as needed, if clinically indicated.
- g.) Study drug infusions are Q3W starting on Day 1. **NOTE:** infusions must be at least 10 days apart; missed doses are not to be made up between scheduled visits, subject is to return for the next scheduled visit/dose. Vital signs (blood pressure, pulse, and temperature) must be recorded prior to, and after each infusion, according to [Section 5.1.6](#).
- h.) If during a home infusion a new safety concern arises, the subject has to attend an on-site visit for an Investigator assessment as soon as feasible.
- i.) See Section 7 for details on safety assessments and AE/SAE reporting.
- j.) Concomitant medications and non-drug therapies must be reported starting with signing of informed consent and ending 28 days after the last dose. If the subject experiences an AE / SAE before the end of the final safety phone call (60 days after last dose), concomitant medications and non-drug therapies may also be collected, if part of the treatment of the AE/SAE.
- k.) If a DLCO is available within 3 months prior to screening, it can be utilized for screening purposes.
- l.) On-treatment PFTs, should be collected pre-dose.

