6.4. Prior and Concomitant Medications

The latest World Health Organization Drug Dictionary (WHODD Global B3 Mar2022, or higher version) will be used to classify prior and concomitant medications by therapeutic class and preferred term.

Prior medication is defined as any medication taken and stopped prior to the first dose of the study drug. Concomitant medication is defined as any medication taken after the first dose of the Confidential

Page 21 of 56

^{*} Major PDs will be reviewed and finalized by following FibroGen medical review process; these five categories may not cover all IPDs.

study drug and before the last dose days +60 days. For subjects who are treated in the OLE, medications that started after 1st dose in the OLE period may be considered as concomitant medication for the OLE period, but not for the double-blind period. Partially or incompletely missing prior/concomitant medication start or stop dates will be imputed (Appendix 1). Table 2 provides the classification guideline when medication starting or ending dates are missing.

Table 2:	Classification	of Dwinn and	Canaamitant	Madiantiana
rabie z:	Ciassification	of Prior and v	Concomitant	vieuications

End Date Start Date	Before start of study drug administration	On or after start of study drug administration	Missing
Before start of study drug administration	Prior	Concomitant	Concomitant
On or after start of study drug administration and before the last dose date +60 days	-	Concomitant	Concomitant
Missing	Prior	Concomitant	Concomitant

Both prior and concomitant medication usage will be summarized by the number (%) of subjects receiving the drug within each therapeutic class and ATC code level 3 and preferred term for the SAF. Multiple usages of the same drug by a patient will be counted only once.

Separate summaries may be provided for prior and concomitant medications of special interest such as the approved IPF medications (pirfenidone and/or nintedanib).

To evaluate the use of co-administered medications that are narrow therapeutic CYP substrates, the concomitant medication for narrow therapeutic index cytochrome P450 substrates will be listed and summarized. The list of related medications will be finalized prior to database lock.

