6.7.1.1.4. Analysis Variable

Change from baseline in all FVC assessments in the double-blind period, including scheduled, unscheduled, and available assessments after treatment discontinuation, up to week 48 during the On-Study period (Section 5.3.1.1), will be included in the analysis.

In the situation where a subject has more than one record of FVC within an analysis visit, the best value will be used for MMRM.

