Appendix 1.2. Missing/Incomplete AE Stop Date

If needed, the following imputation rules apply to the case where the end date is incomplete (i.e., partially missing) for adverse events. Other partial end dates will not be imputed. If the imputed stop date is before the start date (imputed or non-imputed start date), then the imputed stop date will be replaced with the start date.

• Missing day and month, or Missing month only

Confidential Page 39 of 56

December 31 will be assigned to the missing fields. If the imputed stop date is after the date of death, date of death will be used.

• Missing day only

If the month and year of the incomplete stop date are the same as the month and year of the last dose date of double-blind study treatment, then the day of the last dose date will be assigned to the missing day.

If the month and year of the incomplete stop date are different from the month and year of the last dose date of double-blind study treatment, then the minimum of (the last day of the month, end of study date, date of death) will be assigned to the missing day.

Missing year

No imputation.

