Appendix 1.4. Missing/Incomplete Prior or Concomitant Medication Stop Date

Same imputation rules as missing/incomplete AE stop date (Appendix 1.2).

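### Concomitant-medication windows follow the last dose while FVC runs to Week 48, so an antifibrotic started late by a subject who stopped study drug need not be recorded or counted

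*Protocol*

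**What the plan says.** **Recording.** Protocol 5.2.1 requires that concomitant medications "must be recorded from the Screening Visit through 28 days after the last dose". Footnote j, on the concomitant-medication row of the Appendix 1 schedule, agrees: "Concomitant medications and non-drug therapies must be reported starting with signing of informed consent and ending 28 days after the last dose". If an adverse event occurs before the day-60 call, "concomitant medications and nondrug therapies may also be collected, if part of the treatment of the AE/SAE". That extension is optional and limited to drugs given for the event.

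**Classification.** SAP 6.4 defines a concomitant medication as one taken after the first dose of "study drug and before the last dose days +60 days". Table 2 applies the same limit to the start date. A separate sentence keeps drugs started after the first OLE dose out of the double-blind period.

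**Follow-up and FVC.** The protocol synopsis encourages subjects who stop study drug to stay for all visits and assessments. Protocol 3.3.2 lets them take an approved IPF therapy at any time after randomization. SAP 6.7.1.1.4 takes FVC into the primary analysis "including scheduled, unscheduled, and available assessments after treatment discontinuation, up to week 48 during the On-Study period".

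**Use of the data.** SAP 6.4 allows separate summaries of pirfenidone and nintedanib. SAP 6.7.1.4 lists on-study use of an approved IPF therapy (yes/no) among the possible subgroups. Sections 6.7.2.3 and 6.8.1 carry those subgroups to the secondary endpoints and adverse events.

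**Partial stop dates.** SAP Appendix 1.4 applies the adverse-event stop-date rule to medications. Under that rule, when the month is missing, "December 31 will be assigned to the missing fields", limited only by the date of death.

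**The concern.** The medication record follows the last dose of study drug, while the efficacy data follow the visit schedule. The two separate when a subject stops infusions and stays in the study. The trial is meant to study monotherapy and permits antifibrotics, so a reader will want to know how much of the off-treatment FVC was measured on one, and whether such use was balanced between arms. The rules as written neither require that information nor count all of it. Prohibited IPF drugs started late escape in the same way.

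The stop-date rule errs in the other direction. It can turn an antifibrotic that ended before the study into an on-study one.

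**Working it through.** **Inputs.** An infusion in week w has target Day 7w + 1. Required recording ends 28 days later (Protocol 5.2.1) and the SAP window 60 days later (SAP 6.4). Post-baseline spirometry targets are Days 43, 85, 127, 169, 253 and 337 (SAP Table 7).

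**The plan's own figure.** For a 120 mL difference, SD 300 mL, two-sided 0.05 and 90% power: 2 × (1.960 + 1.282)² × (300/120)² ≈ 131.3, so 132 per arm or 264 in total. 264/0.80 = 330, in line with the planned 340. At 136 per arm (340 less 20%) power is about 0.91. None of this uses antifibrotic status.

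**Uncovered days before Week 48.**
- Protocol: 337 − (7w + 1 + 28) = 308 − 7w, not below 0.
- SAP: 337 − (7w + 1 + 60) = 276 − 7w, not below 0.

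| Last dose | Recording ends | SAP window ends | Uncovered days (protocol/SAP) | FVC visits after recording ends | FVC visits after SAP window ends |
|---|---|---|---|---|---|
| Week 12 (Day 85) | Day 113 | Day 145 | 224/192 | 18, 24, 36, 48 | 24, 36, 48 |
| Week 24 (Day 169) | Day 197 | Day 229 | 140/108 | 36, 48 | 36, 48 |
| Week 36 (Day 253) | Day 281 | Day 313 | 56/24 | 48 | 48 |
| Week 39 (Day 274) | Day 302 | Day 334 | 35/3 | 48 | 48 |
| Week 42 (Day 295) | Day 323 | Day 355 | 14/0 | 48 | none |
| Week 45 (Day 316) | Day 344 | Day 376 | 0/0 | none | none |

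The recording gap opens for a last dose at Week 42 or earlier, and the SAP gap at Week 39 or earlier.

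**Number of subjects.** The documents give no figure. As an assumption only: if 5–20% of 340 stop drug but stay, and 10–50% of those start an antifibrotic after the window, the count is 340 × 0.05 × 0.10 = 1.7 up to 340 × 0.20 × 0.50 = 34.

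**Stop dates.** Take a first dose on 15 September 2021 and a prior antifibrotic whose stop is recorded only as 2021. It is imputed to 31 December 2021, and Table 2 calls it concomitant. A stop recorded only as 2020 stays prior. Because Table 2 counts a stop on or after first dose, a first dose on 31 December is caught too. If first doses are spread evenly over a year (assumption), the share of year-only stop dates flagged is (365 − lag)/365, where lag is the days from true stop to first dose: 335/365 = 92% at 30 days, 275/365 = 75% at 90, 185/365 = 51% at 180. A stop date with no year is not imputed, and Table 2 classes it as concomitant.

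**The case against.** A reader might infer that the primary result is compromised. It is not. Both documents use a treatment-policy strategy for stopping treatment (Protocol 8.3.4.1, SAP 6.7.1.1.3), and the model in SAP 6.7.1.1.5 has no term for antifibrotic use.

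A reader might also infer that late starts are always lost. The documents do not support that. The Appendix 1 grid marks concomitant medications at every visit, so a site may still record them, and SAP 5.1 lists everything collected. Footnote j removes the duty but does not forbid the entry. Starts within 28 days of the last dose are covered.

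Nor is every subject who stops early affected. Anyone completing Week 48 may enter the OLE regardless of infusions received. For the final safety assessments, footnote r takes the last dose of such subjects as the last OLE dose. If 5.2.1 is read the same way, their recording gap closes.

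The planned outputs are worded as possibilities, and no sentence ties the on-study-use subgroup to the SAP 6.4 window. That link is the natural reading, not a stated rule.

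The protocol does not expect many subjects to resume an approved therapy, because they tried and stopped one or have none available. That tempers the likely count, but it cannot be verified where recording is not required.

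For prohibited drugs, the analysis consequence is exclusion from the per-protocol set. That set already requires at least 36 weeks of treatment, so the recording gap there is about 56 days at most.

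On stop dates, Protocol 11.3 has incomplete data queried, so few partial dates should remain.

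These points limit the reach of the concern. They do not remove the mismatch between the windows and Week 48.

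**Conclusion.** The mismatch stands for subjects who stop study drug at Week 42 or earlier (Week 39 or earlier for the SAP window), stay in the study and have no later OLE dose. The earlier the stop, the larger the gap. What weakens is the description of approved IPF therapy use, the on-study-use subgroup if it follows SAP 6.4, and the assessment of balance between arms. The report might still show part of this from voluntary entries, so it would be too strong to say that it could not. The range of about 2 to 34 subjects rests wholly on assumed rates, and it would be lower to the extent that such subjects enter the OLE.

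The stop-date fault is real but minor. It needs a partial or missing stop date; the number of these is unknown and probably small.

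The point merits correction because it is cheap and bears on interpretation. It does not put the primary test in doubt.

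**What to change.** 1. **Protocol 5.2.1 and footnote j.** Require recording of at least approved IPF therapies, systemic corticosteroids and the agents in 5.2.2 through the later of the Week 48/ET visit and 28 days after the last double-blind dose, whatever the date of that dose.
2. **SAP 6.4 and Table 2.** End the double-blind concomitant window at the later of last double-blind dose + 60 days and the Week 48/ET visit, but not beyond the first OLE dose. Define the on-study-use subgroup by that window. This change alone helps only for what sites recorded.
3. **SAP Appendix 1.4 (minor).** For an antifibrotic started before Day 1 and not marked ongoing, query an incomplete or missing stop date. If it stays incomplete, cap the imputed stop at the day before first dose, and never before the start date. Use this for classification only, not as evidence that inclusion 8 was met. A cap tied to the inclusion 8 interval would impute eligibility and could hide a deviation that SAP Table 1 is meant to catch.

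The cost is wording in two documents and a few more medication entries at visits already held. With items 1 and 2, the uncovered time before Week 48 is 0 days for every last-dose week among subjects who stay to Week 48. Sample size and power do not change.
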